11. MEASUREMENT OF EFFECT

11.1 Antitumor Effect – Intracranial tumors and Extracranial tumors

Assessment of extracranial disease (by CT scan or other approved modalities) and intracranial disease (by MRI scan with a minimum of 3 mm cuts) will be performed per the schedule in Section 10, Study Calendar.

Investigators may obtain more frequent scans as medically indicated.

Response and progression will be evaluated in this study using the international criteria proposed by the Response Evaluation Criteria in Solid Tumors (RECIST) guideline (version 1.1)³⁹ for all extracranial lesions and modified RECIST 1.1 for all brain lesions (see Section 11.3).

Changes in the largest diameter (unidimensional measurement) of the tumor lesions and the shortest diameter in the case of malignant lymph nodes are used in the RECIST criteria.

Definitions

Evaluable for Target Disease response. Only those participants who have measurable disease present at baseline, have received at least one cycle of therapy, and have had their disease re-evaluated will be considered evaluable for target disease response. These participants will have their response classified according to the definitions stated below. (Note: Participants who exhibit objective disease progression prior to the end of cycle 1 will also be considered evaluable.)

Evaluable Non-Target Disease Response. Participants who have lesions present at baseline that are evaluable but do not meet the definitions of measurable disease, have received at least one cycle (3 weeks) of therapy, and have had their disease re-evaluated will be considered evaluable for non-target disease. The response assessment is based on the presence, absence, or unequivocal progression of the lesions.

Disease Parameters

Measurable disease, intracranial (brain lesions). Measurable brain lesions are defined in this study as those that can be accurately **measured in at least one dimension (longest diameter to be recorded) as ≥ 5 mm with MRI**. All tumor measurements must be recorded in millimeters (or decimal fractions of centimeters).

Note: Brain metastases that have previously been treated with radiation therapy are not considered measurable, unless they have grown and the treating investigator considers them to be refractory to radiation.

Measurable disease, extracranial lesions (including skull, neck, chest abdomen, pelvis, and extremities). Measurable lesions are defined as those that can be accurately measured in at least one dimension (longest diameter to be recorded) as ≥ 20 mm by chest x-ray or ≥ 10 mm with CT scan, MRI, or calipers by clinical exam. All tumor

measurements must be recorded in millimeters (or decimal fractions of centimeters).

Note: Tumor lesions that have previously been treated with radiation therapy are not considered measurable, unless they have grown and the treating investigator considers them to be refractory to radiation.

Malignant lymph nodes. To be considered pathologically enlarged and measurable, a lymph node must be ≥ 15 mm in short axis when assessed by CT scan (CT scan slice thickness recommended to be no greater than 5 mm). At baseline and in follow-up, only the short axis will be measured and followed.

Non-measurable disease. All other lesions (or sites of disease), including small lesions (longest diameter < 5 mm in the brain or < 10 mm in the body, or pathological lymph nodes with ≥ 10 to < 15 mm short axis), are considered non-measurable disease. Bone lesions, leptomeningeal disease, ascites, pleural/pericardial effusions, lymphangitis cutis/pulmonitis, inflammatory breast disease, abdominal masses (not followed by CT or MRI), and cystic lesions are all considered non-measurable.

Note: Cystic lesions that meet the criteria for radiographically defined simple cysts should not be considered as malignant lesions (neither measurable nor non-measurable).

‘Cystic lesions’ thought to represent cystic metastases can be considered as measurable lesions, if they meet the definition of measurability described above. However, if non-cystic lesions are present in the same participant, these are preferred for selection as target lesions.

Target lesions. All measurable lesions up to a maximum of 2 lesions per organ (modification to allow up to 5 lesions in brain) and 8 lesions in total, representative of all involved organs, should be identified as **target lesions** and recorded and measured at baseline. Target lesions should be selected on the basis of their size (lesions with the longest diameter), be representative of all involved organs, but in addition should be those that lend themselves to reproducible repeated measurements. It may be the case that, on occasion, the largest lesion does not lend itself to reproducible measurement in which circumstance the next largest lesion which can be measured reproducibly should be selected. A sum of the diameters (longest for non-nodal lesions, short axis for nodal lesions) for all target lesions will be calculated and reported as the baseline sum diameters. If lymph nodes are to be included in the sum, then only the short axis is added into the sum. The baseline sum diameters will be used as reference to further characterize any objective tumor regression in the measurable dimension of the disease.

Non-target lesions. All other lesions (or sites of disease) including any measurable lesions over and above the 5 target lesions should be identified as **non-target lesions** and should also be recorded at baseline. Measurements of these lesions are not required, but the presence, absence, or in rare cases unequivocal progression of each should be noted throughout follow up.

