10. STUDY CALENDAR

10.1 Scheduling windows

Baseline evaluations are to be conducted within 1 week prior to start of protocol therapy. Scans and x-rays must be done <4 weeks prior to the start of therapy. If the participant's condition is deteriorating, laboratory evaluations should be repeated within 48 hours prior to initiation of the next cycle of therapy. Assessments must be performed prior to administration of any study agent. Study assessments and agents should be administered within + 7 days of the protocol-specified date for Days 1-309, and within + 14 days of the protocol-specified date for Days 337-673.

	Baseline	Cycles 1-4: Induction				Cycles 5-13			End of Treatment (EOT) Cycle 14	Follow-Up Visit #1	Follow-Up Visits #2-4 ⁱ	Final Follow-Up Visit ^j	EDC Timepoints
		Day 1	Day 22	Day 43	Day 64	Day: 85 169 253	Day: 113 197 281	Day: 141 225 309	Day 337 or sooner	Within 30 days post EOT	Day: 421 505 589	Day 673 or sooner	
Troriluzole or placebo^T (continuous oral twice daily dosing)		T-----T											Medication Diary Documentation Day 43, 85, 169, 253, EOT
Ipilimumab and Nivolumab		I+N	I+N	I+N	I+N								Day 1, 22, 43, 64
Nivolumab						N	N	N	N				Day 85, 113, 141, 169, 197, 225, 253, 281, 309
Informed consent	X												N/A
Demographics	X												Baseline
Medical history, including BRAF mutational status	X												Baseline
Physical exam	X	X	X	X	X	X	X	X	X	X	X	X	Baseline
Vital signs	X	X	X	X	X	X	X	X	X	X	X	X	Baseline
Height	X												Baseline

	Baseline	Cycles 1-4: Induction				Cycles 5-13			End of Treatment (EOT) Cycle 14	Follow-Up Visit #1	Follow-Up Visits #2-4 ⁱ	Final Follow-Up Visit ^j	EDC Timepoints
		Day 1	Day 22	Day 43	Day 64	Day: 85 169 253	Day: 113 197 281	Day: 141 225 309	Day 337 or sooner	Within 30 days post EOT	Day: 421 505 589	Day 673 or sooner	
Weight	x	x	x	x	x								Baseline
Performance status	x	x				x			x	x			Baseline, EOT
CBC w/diff, plts and CMP ^a	x	x	x	x	x	x	x	x	x	x	x	x	N/A
Gamma-glutamyl transferase (GGT), LDH, amylase, lipase, TSH, free T4 ^b	x					x			x	x			GGT only: Baseline, Day 85, 169, 253, 337
B-HCG ^c , pro-BNP, troponin-T	x												N/A
EKG	x					x							Baseline, Day 85, 169, 253. If EKG is performed during any other Cycle, it must be captured in EDC.
MRI Brain (with and without gadolinium contrast) for intra-	x			x		x			x				Baseline, Day 43, 85, 169, 253. If Intracranial Tumor Measurements are performed

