13.6 Analysis of Secondary Endpoints

Overall Survival

Overall Survival (OS) is defined as the time from randomization (or registration) to death due to

any cause, or censored at date last known alive. Estimates of overall survival will also be from a PHMC model (Section 13.5). Long-term survival estimates and comparisons will be based on the incidence portion of the model; hazards of death will be based on the latency portion of the model. The distribution of deaths will be summarized using marginal survival function curves.

Intracranial or Extracranial Response

The proportion of patients in each treatment arm with intracranial response (RECIST) will be presented with exact, 90% binomial confidence intervals. The randomized treatment arms will be compared using Fisher's exact test. Comparable comparisons will be conducted for extracranial response (RECIST).

Intracranial or Extracranial PFS

Extracranial PFS is defined as the time from first dose of study therapy to documented extracranial progression (per RECIST) or death, whichever occurs first. Intracranial PFS is defined as the time from first dose of study therapy to documented intracranial progression or death, whichever occurs first. For both endpoints, the follow-up of patients who have neither died nor progressed at the time of analysis will be censored at the date of last adequate disease assessment. Treatment comparisons of intracranial or extracranial PFS will be based on PHMC methods outlined in Section 13.5. Point estimates at 6 months will be presented with confidence intervals.

Safety Data

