13.7 Reporting and Exclusions

Evaluation of Toxicity

All participants will be evaluable for toxicity from the time of their first treatment.

Evaluation of the Primary Efficacy Endpoint

The analysis of the primary endpoint will be conducted using the intention-to-treat principal, meaning all randomized patients will be evaluated according to the treatment assigned at the time of enrollment.

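### Sections 11.1 and 13.6 leave the denominator of the response rates unsettled, and nothing says that a patient with no post-baseline assessment counts as a non-responder

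*Combined protocol and SAP*

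**What the plan says.** Section 11.1 defines who can be classified for target-disease response: patients with measurable disease at baseline who received one cycle or more and "have had their disease re-evaluated will be considered evaluable for target disease response". One exception follows: "Participants who exhibit objective disease progression prior to the end of cycle 1 will also be considered evaluable". A parallel definition for non-target disease also requires one cycle and a re-evaluation.

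Section 13.6 gives the analysis: "The proportion of patients in each treatment arm with intracranial response (RECIST) will be presented with exact, 90% binomial confidence intervals". The arms are then compared by Fisher's exact test. For the body compartment, "Comparable comparisons will be conducted for extracranial response (RECIST"). Section 13.6 neither refers to the evaluable set nor says how a patient without a response classification is counted.

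Section 13.7 names an analysis principle for one endpoint: "The analysis of the primary endpoint will be conducted using the intention-to-treat principal". It names none for response. The best-overall-response table in 11.3 has no category for a patient who could not be evaluated.

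**The concern.** Receiving a full cycle and being re-imaged are both events after randomization. A denominator restricted to patients who meet them no longer compares the groups formed by randomization. A patient who dies or withdraws before any scan has not responded, yet would be removed from the calculation instead of lowering the rate. The arm with more such losses gains the most.

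The losses could differ between arms, because one arm receives an added active drug. What is at stake is the between-arm comparison of intracranial and extracranial response. Both are secondary endpoints that would be read alongside PFS in a signal-detection trial. If the denominator is left open, it could also be chosen after the results are known.

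**Working it through.** **1. The texts side by side.**

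| Place | What it settles | What it leaves open |
|---|---|---|
| 11.1 | Whose response is classified | Whether this set is the analysis denominator |
| 13.6 | Proportion by treatment arm, exact 90% interval, Fisher test | How unclassified patients count |
| 13.7 | Intention-to-treat for the primary endpoint | Population for response |
| 11.3 table | Overall response from target, non-target and new lesions | Patients with no assessment |

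Section 13.6 cannot mean every patient for extracranial target response, because eligibility item 3.102 does not require measurable extracranial disease. Some baseline restriction is needed there, and it is not written down.

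**2. Who would be lost if 11.1 governs.** In the Section 10 calendar, the data-entry column for brain MRI begins "Baseline, Day 43, 85, 169, 253. If Intracranial Tumor Measurements are performed", so the first scheduled on-treatment MRI is Day 43. The first scheduled body CT is Day 85. The calendar also marks MRI and CT at the End of Treatment visit, which is Day 337 or earlier if treatment stops. A patient who completes a cycle, stops for toxicity and attends that visit is re-imaged and stays evaluable. Those who fall out are:

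- patients who die, withdraw or are lost before any post-baseline scan;
- patients who stop before completing one cycle without objective progression, whether or not they are scanned;
- randomized patients who never start therapy, whom 4.1 and 4.3 take off study.

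**3. Size.** The plan gives no expected response rate, power or non-evaluable count for this comparison, so there is no figure of its own to reproduce. Inputs from the documents: up to 90 randomized in equal proportions (13.1, 13.2), so n = 45 per arm. Assumed inputs: r = 20 responders per arm and m = 2 to 6 patients lost in an arm.

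All randomized: r/n = 20/45 = 44.4%. Evaluable only: r/(n − m).

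| Lost, m | Rate | Change from 44.4% |
|---|---|---|
| 2 | 20/43 = 46.5% | +2.1 points |
| 6 | 20/39 = 51.3% | +6.8 points |

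If the arm given troriluzole (INT) loses 6 and the placebo arm (INP) loses 2, two identical true rates appear as 51.3% and 46.5%. That is a false difference of 4.8 points, with two-sided Fisher p = 0.83.

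**4. Can the choice change a reading?** Assume 22 responders in INP and 28 in INT.

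| Denominator | INP | INT | Fisher p |
|---|---|---|---|
| All randomized | 22/45 = 48.9% | 28/45 = 62.2% | 0.29 |
| 2 INP, 6 INT lost | 22/43 = 51.2% | 28/39 = 71.8% | 0.071 |
| 2 INP, 7 INT lost | 22/43 = 51.2% | 28/38 = 73.7% | 0.043 |

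It can, but only when unequal losses are combined with a difference in responder counts that is already present. Both are assumptions.

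**The case against.** The strongest reply is that 13.6 already answers the question. It is the analysis section, it speaks of the patients in each arm, and it compares the randomized arms. Section 11.1 is a measurement section that names no analysis set, and 13.7 lists no response exclusion. On that reading nobody leaves the denominator. This stands as far as it goes: a reader might infer from 11.1 that early dropouts are certain to be removed, and the documents do not support that. They also do not say the opposite. No text counts an unclassified patient as a non-responder, and 11.1 leaves such a patient with no response category to enter.

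The second reply concerns who is lost. A reader might infer that everyone who stops for toxicity before Day 43 or Day 85 is excluded. The End of Treatment imaging contradicts that. In addition, 5.10 limits removal from study to loss to follow-up, withdrawal of consent and death. Section 11.1 allows extra scans, and 11.3 asks for efforts to document progression after treatment stops. This narrows the group considerably but does not recover deaths, withdrawals or missed visits.

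Third, imbalance between arms is possible but not established. Section 6.3 lets the checkpoint inhibitors continue when troriluzole is held or discontinued for an event not attributed to them, so intolerance of troriluzole need not end treatment or imaging before the first MRI. The 6-versus-2 split has no source in the documents.

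**Conclusion.** The point holds as a gap in specification: 11.1 and 13.6 do not agree on a response denominator, and no rule covers patients without a post-baseline assessment. If the 11.1 definition were used, the comparison would be conditioned on post-randomization events and would favour the arm with more early unscanned losses.

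The size depends on a number that the documents do not give. Under the assumed 2 to 6 losses per arm of 45, an arm's rate rises by about 2 to 7 points, and a 6-versus-2 split gives a false gap of about 5 points. That gap alone would not reach significance. Fewer or balanced losses would make the between-arm effect smaller.

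The effect is confined to the secondary response endpoints. Global PFS is analysed by intention-to-treat, and early deaths count as events in global, intracranial and extracranial PFS, so early failures remain visible there. The change is worth making because it is cheap and removes an avoidable bias; the main conclusion does not depend on it.

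**What to change.** Add to 13.6 that the main analysis of intracranial response uses all randomized patients according to assigned arm. For extracranial response, it uses all randomized patients with measurable extracranial disease at baseline. In both, a patient with no post-baseline assessment counts as a non-responder.

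Keep the 11.1 evaluable set as a supporting analysis. Report the number of non-evaluable patients and the reasons by arm, so that any imbalance can be seen. A cross-reference from 11.1 to 13.6 would make clear that evaluability governs classification, not the denominator.

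The cost is a sentence or two of text and slightly lower reported response rates. No new data, visits or patients are needed.

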11.3 Response Criteria: **modified RECIST version 1.1**

Response and progression will be evaluated in this study using the international criteria proposed by the Response Evaluation Criteria in Solid Tumors (RECIST) guideline (version 1.1);³⁹ however there will be **two modifications for assessment of brain lesions on this protocol:**

- 1) modification to allow up to five target lesions in the brain (all other organs continue to have a maximum of 2 target lesions), and the maximum number of target lesions globally may be up to 10 lesions.
- 2) to include target lesions in the brain measuring ≥ 5 mm in their longest diameter as seen on thin cut MRI (slice thickness ≤ 2 mm), as described previously in other brain

metastases trials.^{3,40,41}

Changes in the largest diameter (unidimensional measurement) of the tumor lesions and the shortest diameter in the case of malignant lymph nodes are used in the RECIST criteria.

Evaluation of Target Lesions

Complete Response (CR): Disappearance of all target lesions. Any pathological lymph nodes (whether target or non-target) must have reduction in short axis to <10 mm.

Partial Response (PR): At least a 30% decrease in the sum of the diameters of target lesions, taking as reference the baseline sum diameters.

Progressive Disease (PD): At least a 20% increase in the sum of the diameters of target lesions, taking as reference the smallest sum on study (this includes the baseline sum if that is the smallest on study). In addition to the relative increase of 20%, the sum must also demonstrate an absolute increase of at least 5 mm. (Note: the appearance of one or more new lesions is also considered progression).

Stable Disease (SD): Neither sufficient shrinkage to qualify for PR nor sufficient increase to qualify for PD, taking as reference the smallest sum diameters while on study.

Evaluation of Non-Target Lesions

Complete Response (CR): Disappearance of all non-target lesions. All lymph nodes must be non-pathological in size (<10 mm short axis).

Non-CR/Non-PD: Persistence of one or more non-target lesion(s).

Progressive Disease (PD): Appearance of one or more new lesions and/or *unequivocal progression* of existing non-target lesions. *Unequivocal progression* should not normally trump target lesion status. It must be representative of overall disease status change, not a single lesion increase.

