11.5 Progression-Free Survival

Progression-Free Survival: Progression-Free Survival (PFS) is defined as the time from randomization (or registration) to the earlier of progression in the intracranial or extracranial sites or death due to any cause. Herein, the term “PFS” refers to PFS in both the intracranial and extracranial compartments (global). The follow-up of participants alive without disease progression is censored at date of last disease evaluation.

Time to Progression: Time to Progression (TTP) is defined as the time from randomization (or registration) to progression, or censored at date of last disease evaluation for those without progression reported.

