Following the Safety Run-in, all participants will be enrolled on the randomized portion of the study.

Primary Endpoint. The primary endpoint of the study is global progression-free survival in patients with melanoma brain metastases who are treated with INT vs. INP. Of particular interest will be PFS at 6 months.

PFS is defined as the time from random assignment to the earlier of death or documented disease progression in the intracranial or extracranial compartments. The follow-up of patients who have neither died nor progressed will be censored at the date of the last follow-up visit.

Secondary Endpoints. The secondary objectives and their associated endpoints evaluate other important clinical outcomes, including overall survival (OS), intracranial response rate (RR) and

PFS, extracranial RR and PFS, and safety (number of participants experiencing adverse events, particularly neurologic events). We will also investigate:

- tolerability (number of induction cycles administered, number of maintenance cycles administered)
- use of corticosteroids for management of symptomatic cerebral edema (number of participants)
- use of corticosteroids for management of immune related adverse events (number of participants who require prednisone ≥ 1 mg/kg or equivalent)
- frequency of clinically-indicated stereotactic radiation therapy to the brain on study (number of patients, number of instances and number of lesions irradiated)
- frequency of clinically-indicated surgical intervention to the brain on study (number of participants)

Planned subgroup analyses according to baseline characteristics:

- Prior anti-PD-1 exposure (yes vs. no – if yes then adjuvant vs. metastatic setting)
- Prior ipilimumab exposure (yes vs. no)
- Age (<65 years vs 65 years or older)
- ECOG (0 vs 1)
- LDH at baseline (normal vs. elevated)
- Number of brain metastases (<3 vs 3 or more)
- Brain-directed stereotactic radiation therapy prior to study entry (yes vs. no)
- Craniotomy prior to study entry (yes vs. no)

Planned subgroup analyses according to on-study events:

- On-study brain-directed stereotactic radiation therapy (yes vs. no)

Exploratory Endpoints:

- associations between BRAF/NRAS mutation status and response endpoints, as well as tissue biomarker profiles between paired tissues from extracranial and intracranial metastases from individual patients, where available

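### The target-lesion rules in 11.1 and 11.3 give one sum over brain and body, but the primary endpoint needs progression judged in each compartment

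*Combined protocol and SAP*

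**What the plan says.** **Measurement rules.** Section 11.1 selects target lesions from one list across organs, with up to five in the brain and "8 lesions in total, representative of all involved organs". It then forms a sum of diameters that "for all target lesions will be calculated and reported as the baseline sum diameters". Section 11.3 defines partial response as "At least a 30% decrease in the sum of the diameters of target lesions" and progression as "At least a 20% increase in the sum of the diameters of target lesions", measured from the smallest sum on study, and adds that "the sum must also demonstrate an absolute increase of at least 5 mm". It lists two brain modifications, on the number of target lesions and on the 5 mm minimum size. Neither creates a brain sum. The best-overall-response table has one target-lesion column.

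**Endpoints.** Section 11.5 defines PFS as time to the "earlier of progression in the intracranial or extracranial sites or death due to any cause". Section 13.1 defines the primary endpoint by the earlier of death or "documented disease progression in the intracranial or extracranial compartments". Section 13.6 compares intracranial and extracranial response, and intracranial and extracranial PFS, as separate endpoints.

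**Text pointing towards compartments.** The opening of 11.1 assigns RECIST 1.1 to extracranial lesions and modified RECIST 1.1 to brain lesions. The Section 10 calendar has separate rows for brain MRI and body CT measurements. Day 43 has a brain MRI but no body scan.

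**The concern.** The endpoint asks whether either compartment has progressed. The written measurement rule asks whether the total across both has grown enough. The two questions can have different answers when brain and body targets change by different amounts, because a stable or shrinking body sum offsets growth in the brain.

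The consequence is that the same scans may be a PFS event at one site and stable disease at another. Section 11.6 requires no central review, so no planned central reading would bring the sites into line. The randomized part has at most 90 patients, and 13.4 places the futility look at about 15 PFS events, so even a few reclassified or delayed events could matter. The brain is also the compartment of main interest: 2.7 rests part of the rationale on riluzole crossing the blood-brain barrier.

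**Working it through.** The plan gives no figure on this point to reproduce. The check applies its own thresholds to a pooled sum and to a sum per compartment.

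**Inputs from 11.3.** Progression (PD): at least +20% and at least +5 mm over the smallest sum. Partial response (PR): at least 30% below the baseline sum.

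**Assumed inputs.** All lesion sizes and brain shares below are illustrative; the documents give none.

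**1. Brain growth needed under pooling.** Let w be the brain share of the reference sum, h the fractional change in the body sum and g the fractional change in the brain sum. The pooled change is w·g + (1 − w)·h. Setting this to at least 0.20 gives

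g ≥ (0.20 − (1 − w)·h) / w

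| Brain share w | Body stable (h = 0) | Body down 30% (h = −0.30) |
|---|---|---|
| 1.00 | +20% | +20% |
| 0.75 | +27% | +37% |
| 0.50 | +40% | +70% |
| 0.25 | +80% | +170% |
| 0.10 | +200% | +470% |

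For example, at w = 0.50 and h = −0.30: (0.20 + 0.50 × 0.30)/0.50 = 0.70. On a separate brain sum the requirement is always +20%. The 5 mm rule applies in addition in every case. With no body targets (w = 1) the two rules agree.

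**2. The same measurements under each reading.**

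| Brain (mm) | Body (mm) | Pooled reading | By compartment |
|---|---|---|---|
| 22 → 44 | 100 → 100 | (144 − 122)/122 = +18.0%, not PD | brain +100%, +22 mm: PD |
| 22 → 44 | 100 → 70 | (114 − 122)/122 = −6.6%, stable | brain PD, as above |
| 10 → 15 | 80 → 40 | (55 − 90)/90 = −38.9%, PR | brain +50%, +5 mm: PD |
| 20 → 12 | 60 → 60 | (72 − 80)/80 = −10%, stable | brain −40%: PR |
| 10 → 12.5 | 12 → 14.5 | (27 − 22)/22 = +22.7%, +5 mm: PD | each +2.5 mm: not PD |

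The first three rows hide brain progression and the fourth hides a brain response. The last goes the other way: pooling calls progression when neither compartment meets the 5 mm rule.

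**3. Day 43.** Brain MRI is scheduled and body CT is not. The first scheduled on-treatment body scan is Day 85. No current pooled sum can be formed from the scheduled Day 43 scans, and no rule says whether to carry the baseline body sum forward. Growth of brain targets at that visit has a clear test only if a brain sum exists.

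**4. Lesion counts.** Section 11.1 caps targets at eight in total, then treats measurable lesions beyond five as non-target. Section 11.3 says "the maximum number of target lesions globally may be up to 10 lesions". The three counts disagree about which lesions enter the sum.

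**The case against.** The strongest reply is that the protocol already works by compartment. Section 11.1 names a criteria set for each, 13.6 refers to RECIST for response and for extracranial progression, the calendar collects the measurements separately, and a brain-only scan at Day 43 makes little sense under pooling. Sections 5.6 and 5.7 also speak of progression in the brain. The endpoint definition could be read as governing the generic sum sentence. This stands as evidence of intent, and a reader who inferred that the plan has settled on pooling would go too far. It does not supply the missing rule: 11.1 sends the reader to 11.3, which offers two modifications and one sum.

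A second reply is that few participants are affected. This also stands in part. Section 3.1 does not require measurable extracranial disease, and participants without body targets are unaffected. New lesions and unequivocal non-target progression count whatever the sum. Sections 2.1 and 2.5 report that responses in brain and body were concordant in the great majority of patients in the reference study. Hidden events therefore need discordant target changes.

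A reader might also infer that the primary comparison is biased towards one arm, or that brain events are systematically lost. The documents do not support either. Part II is double-blind, so a site's choice of reading should not depend on allocation, and the errors run in both directions. Nor do the documents show that brain targets are small beside body targets: up to five are allowed in the brain against two in any other organ. The tumor CRF is not among the documents, so it is not established that sites record only one sum.

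**Conclusion.** The concern holds as an internal inconsistency: the written sum rule and the endpoint definition can classify the same scans differently, and no section says which applies. The brain growth needed for target progression is +20% on a brain sum. On a pooled sum with a stable body it ranges from +27% to +200% for assumed brain shares of 0.75 to 0.10.

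The effect is confined to participants with target lesions in both compartments and to classification by target measurements. How many such participants there will be, their brain shares and how often the compartments diverge are not given, so the effect on PFS event counts or power cannot be computed. The likely result is mostly noise and some mistimed events. The point should be fixed, but it is not a fundamental flaw in the primary analysis.

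**What to change.** In 11.1 and 11.3:

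- Define two sums, one over brain targets and one over extracranial targets, each with its own baseline and nadir.
- Apply the CR, PR, SD and PD thresholds, including the 5 mm rule, and the response table within each compartment.
- Declare global progression at the first PD in either compartment, in line with 11.5 and 13.1.
- Reconcile the target-lesion counts of 5, 8 and 10 in the same edit.

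Record both sums on the tumor CRF, and recompute them for enrolled participants before unblinding.

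The cost is a few sentences of protocol text and two CRF fields. The calendar already captures intracranial and extracranial measurements as separate items, so no new scans are needed. The change concerns endpoint classification only.
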